4.3 Participant Selection

Participant selection was done by the study sites. However, the Data Coordinating Center provided lists of children to prioritize based on gestational age. Additionally, the Data Coordinating Center create and reviewed reports of enrollment by site, sex and gestational age to ensure balanced enrollment between treatment groups.

4.4 Masking and Data Lock

Masking was maintained from the larger ASPIRIN Trial through follow-up. As such, throughout the study, research staff and local health providers will be blinded to treatment status of the mother. Data regarding the subject's allocation will be held and protected centrally and will not be made available to participants or their families.

Data Lock: Data will be locked at the site level with final analysis data sets generated and locked once data from all sites have been received and all queries processed. For each site, data collection for the protocol will stop approximately 2 months after the last child was randomized into the study at that site. Site will transmit all data forms to the central site within one months of this date, and data will be locked two to three months post last follow-up visit. The study will not be unmasked until after data lock.

5. ANALYSIS POPULATIONS

Intention to Treat (ITT) Population

The primary analysis population will be the intention to treat population, which includes all eligible and enrolled follow-up participants. All participants will be assigned to the arm to which they were randomized irrespective of treatment received. Unless specified otherwise, all participants with data available will be included in analyses using this population. Missing data will be considered missing at random and not included. This population will also be used for many of the secondary analyses.

Per Protocol (PP) Population

This population is based on the main study PP population and will be used to conduct sensitivity analyses for the primary outcome. This population will exclude all or part of the data obtained from any eligible, randomized participants that did not receive at least 90% of the full amount of intended

randomized study therapy or are considered to have substantially deviated from the protocol in a manner that may impact study outcome or treatment receipt. The population will also exclude individuals who were randomized after 10 weeks, 6 days gestational age. Participants will be grouped by actual treatment received. Treatment receipt reasons and substantial deviations that will lead to exclusion include:

- Documented receipt of aspirin while on study outside of assigned study drug as identified by a reported protocol deviation
- Not receiving treatment after randomization: All data from these participants will be excluded.
- Receipt of less than 90% of planned total doses after randomization where the number of planned doses will be calculated as those expected between randomization and the earliest of end of pregnancy and 36 0/7 weeks GA irrespective of if study drug administration was prematurely discontinued for any reason prior to that point: All data from these participants will be excluded.

Receiving more than the planned total doses of study drug will generally NOT be an exclusion criterion for the PP population. Additional exclusion reasons may be identified after completion of participant enrollment. Any participant deviations that will exclude participants or their data from the PP analyses will be identified by the study team, prior to review of efficacy and safety data, as a part of a masked data review to reduce the opportunity for introducing of bias and will be documented in an addendum to this analysis plan.

6. SAMPLE SIZE DETERMINATION

The primary outcome of BSID-III score is assumed to have a mean scaled score of 100 and standard deviation of 15.47. Assuming a non-inferiority margin of 4 points is clinically significant, and the true effect of LDA is not more than a 1 point decrease, a total sample size of 620 children with a 1:1 allocation (310 in each group will have 80% power for a one-sided test for non-inferiority with $\alpha=0.05$. Conditional on non-inferiority being observed, this sample size will also provide over 90% power at $\alpha=0.05$ to detect a different of 4 points between LDA exposed and non-exposed children based on a two-sided test for the secondary hypothesis.

Analyses of secondary outcomes will be exploratory in nature and generally will focus on estimation of effect sizes and generation of hypotheses.

7. STATISTICAL / ANALYTICAL ISSUES

7.1 General Rules

All statistical computations will be performed and data summaries will be created using SAS 9.3 or higher. If additional statistical packages are required, these will be discussed in the study report. For summaries of study data, categorical measures will be summarized in tables listing the frequency and the percentage of participants in each study arm; continuous data will be summarized by presenting mean, standard deviation, median, minimum, and maximum; and ordinal data will be summarized by only presenting median and the limits of the interquartile range.

7.2 Adjustments for Covariates

While this is a cohort study conducted on a subset of participants from a randomized trial, covariates may be adjusted for in the analyses if treatment imbalance is present. Covariates for consideration include gender, breast feeding, stunting, weight, and family care indicators. These factors will also be explored in secondary analyses for modifying/mediation effects.

7.3 Missing Data Approaches:

The primary reason for missing data will be participant withdrew consent or the child aging out. All missing data will be excluded from primary analyses.

7.4 Multicenter Studies

For this multicenter study, randomization of study participants was stratified within site. Consequently, for all test-based analyses of treatment effect and model-based primary and secondary analyses, site will be included as a fixed effect in the models. As exploratory analyses, analyses, particularly those providing estimate of treatment effect, will be conducted by region: Africa, Asia, and Guatemala.

7.5 Multiple Comparisons and Multiplicity

There is only one formal hypothesis test for this study. As such, a statistical test will be conducted at a 5% type I error rate (two-sided) for the primary efficacy measure, and no adjustments for multiplicity will be made. All analyses of secondary outcomes are exploratory in nature; therefore, p-values and confidence intervals are provided for descriptive purposes only. All p-values provided for any baseline and demographic characteristics and safety parameters will be for descriptive purposes only. As such, unless otherwise specified, p-values presented will be on a per analysis basis, with no further control for multiple tests.

7.6 Masked Data Review

A masked data review is unlikely to be needed for this study. Details of any masked data review conducted and resulting decisions will be described in a SAP addendum.

8. STUDY PARTICIPANTS, TREATMENT EXPOSURE AND COMPLIANCE

8.1 Participant Disposition

Participant eligibility status will be summarized by study arm and overall disposition of study participants will be described using a standard CONSORT diagram.

8.2 Protocol Deviations

Any protocol deviations reported will be reviewed to determine if any data need to be excluded from analysis.

8.3 Demographic and Baseline Characteristics

Demographic and baseline clinical characteristics for the study participants will be summarized by treatment group using the general analysis rules describe above for the ITT and PP populations.

Variables of interest include the same characteristics as from the main trial: maternal age, maternal education, gravidity, maternal weight and BMI, previous pregnancy loss, number of antenatal care visits, delivery attendant, delivery location, and type of delivery.

9. NON-INFERIORITY AND EFFICACY ANALYSES

9.1 Overview of Efficacy Analysis Methods

Efficacy analyses will be performed using the ITT population. Sensitivity analyses will be performed using the per-protocol population as detailed below. The data will be summarized by treatment arm, overall and by region. All model-based analyses and test-statistics examining the treatment effect will adjust for covariates as specified in sections 7.2 and 7.3. Additional details are presented in the sections below.

9.2 Definition of Analysis Variables

The following table defines each of the effectiveness and process analysis variables.

Variable	Type	Definition
Primary Outcome		
BSID-III scores	Continuous	
The unit of analysis is the child enrolled in the study. The three associated outcomes will be the mean scaled composite cognitive, language and motor BSID-III scores assessed and reported at 36 months of life (+/- 3 months). The cognitive score will be considered primary.
 
Raw scores will be summarized but not analyzed.
 
Analysis Population: ITT

Low BSID-III scores	Binary	
The unit of analysis is the child enrolled in the study. The three associate outcomes will be whether the child scored less than an 85 on each of the composite cognitive, language and motor BSID-III scaled composite scores assessed at 36 months of life (+/- 3 months).
 
Cognitive scores < 54 and motor scores < 45 will have missing associated binary outcomes.
 
Analysis Population: ITT

Secondary Outcome		
ASQ-3 scores	Continuous	
The unit of analysis is the child enrolled in the study. The 5 associated outcomes will be the scores of the components of the ASQ-3 assessment, including communication, gross motor, fine motor, problem solving and personal-social.
 
Analysis Population: ITT

Variable	Type	Definition
Low ASQ-3 scores	Binary	
The unit of analysis is the child enrolled in the study. The outcome will be whether the child scored 2 standard deviations less than the mean on each of the communication, gross motor, fine motor, problem solving and personal-social ASQ-3 scores assessed at 36 months of life (+/- 3 months). Established, published cut-offs using US standards will be used as there are no region specific cut-offs established for the study sites.
 
Analysis Population: ITT

9.4 Primary Analysis

The primary analysis will compare the BSID-III composite scores between the two treatment arms using a non-inferiority test. For each of the three BSID-III composite scores, a mean difference between treatment arms and its associated 90% confidence interval will be calculated. If the lower bound of the 90% confidence interval is greater than -4, then the treatment is assumed to be non-inferior to placebo. If non-inferiority is assumed, a one-sided t-test will be run to test the benefit of treatment compared to placebo. All analyses will be modeled based controlling for site as the original randomization stratification factor. For each outcome, the adjusted mean difference between treatment groups and the associated 90% confidence interval based on an ANCOVA model will be calculated and presented. Secondary models will include region and a region by treatment interaction in order to get region specific treatment effect estimates.

Prior to conducting formal analyses baseline demographic characteristics and key clinical measures will be compared between the mothers who participated in the two treatment arms using contingency table approaches for categorical variables and analysis of variance models and t-tests for continuous variables. For all of these analyses, comparisons will be made within Global Network sites and overall across the sites controlling for site in the models.

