Poor nutrition and growth limitations in the fetus/infant have also been associated with impairments in neurodevelopment¹⁵. In Guatemala, a cohort study found stunting, which is reflective of perinatal nutrition, to be prevalent in 47% of newborns; 53% at 3 months of age and 56% at 6 months of age²⁴. This study concluded that growth failure in infants was predicted by growth failure in fetal life, thus indicating the importance of maternal interventions. Data from other Global Network participating sites (Guatemala, Democratic Republic of Congo, Zambia and Pakistan) also found strikingly high rates of stunting ranging from 44% to 66%, among infants and toddlers²⁵. Malnutrition, which also includes being overweight and obese, are known inflammatory processes that can potentially impact neurodevelopment. These conditions are increasingly more

common to low and middle income countries ²⁶. Other newborn exposures including exclusive breastfeeding, stunting, as well as caregiver factors such as maternal/parental education, mental health, and home environment. Poverty additionally contributes to the attainment of optimal neurodevelopment. As such, any study of neurodevelopment should at least document these potential confounders.

1.4 IMPLICATIONS OF ASPIRIN ON NEURODEVELOPMENT:

1.4.1 Biologic Rationale:

In a review of 37 papers, Nist and Pickler¹⁶ identified a series of inflammatory mediators (interleukin (IL)-6, IL-1 β , IL-8, and tumor necrosis factor (TNF)- α & others) that were all associated with neurodevelopmental delay in children. Specifically both inflammatory mediators and hypertensive disorders have been shown to negatively affect neurotrophins and other neuroproteins that are critical in the neuronal programming and development²⁷. Thus, there is direct biological plausibility of maternal inflammation hindering normal child neurodevelopment. Of particular interest is that many of these same inflammatory mediators have been implicated as playing crucial roles in spontaneous preterm birth and maternal hypertensive disorders of pregnancy (HDP).

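### The SAP describes the covariates of the primary model in three different ways, and none of the three lists includes a maternal baseline variable; one pre-specified baseline-adjusted ANCOVA would settle this and gain precision

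*Combined protocol and SAP*

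**What the plan says.** Three places in the SAP bear on the primary model.

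- **9.4 (Primary Analysis):** "All analyses will be modeled based controlling for site as the original randomization stratification factor". Section 7.4 agrees: "site will be included as a fixed effect in the models". No other covariate is named.
- **9.1 with 7.2:** "All model-based analyses and test-statistics examining the treatment effect will adjust for covariates as specified in sections 7.2 and 7.3". Section 7.3 concerns missing data and lists no covariates, so only 7.2 carries content here. It makes adjustment optional and dependent on the data: "covariates may be adjusted for in the analyses if treatment imbalance is present". The candidates follow: "Covariates for consideration include gender, breast feeding, stunting, weight, and family care indicators".
- **Footnote to Tables 5a and 5b:** the BSID-III estimates come from a regression with child sex, stunting, breastfeeding and the family care items alongside site.

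Maternal data appear elsewhere. SAP 8.3 summarises them: "Variables of interest include the same characteristics as from the main trial: maternal age, maternal education, gravidity, maternal weight and BMI", together with previous pregnancy loss. SAP 9.4 compares the mothers' baseline characteristics between arms before the formal analysis, but states no consequence for the model. Protocol 1.3 lists "caregiver factors such as maternal/parental education, mental health, and home environment" among the influences on development and treats such factors as potential confounders that a study should at least document. Child sex is watched during enrolment through "reports of enrollment by site, sex and gestational age to ensure balanced enrollment between treatment groups" (SAP 4.3).

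**The concern.** The non-inferiority verdict turns on the lower limit of one confidence interval, so the model that produces it should be fixed and unambiguous. As written, three analysts could fit three models: site alone, site plus whatever is judged imbalanced, or the table-footnote model.

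The choice of candidates is also the wrong way round. Four of the five in 7.2 (breastfeeding, stunting, weight, family care indicators) are measured after the mother was randomised and could lie on the path from aspirin to the score; 7.2 itself proposes to examine them for mediation. Maternal characteristics from the main trial, which can be related to the score without being affected by treatment, are on none of the lists. If maternal education or BMI differed between arms, the planned comparison would show it, but no listed covariate would address it. The trigger in 7.2 has no threshold, so adjustment would be decided after looking at the data.

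**Working it through.** **Inputs.** Margin 4 points, assumed true difference -1, 310 per arm, one-sided 5% (lower limit of a 90% interval): SAP 6 and 9.4. SD 15: protocol 3.2. SAP 6 prints the SD as 15.47, apparently 15 with reference number 47 run into it; 15.47 would need 658 children and does not reproduce the stated 620. The share of within-site variance explained by added covariates, R², is not in the documents and is varied. SD 15 is taken as the residual SD after site.

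**Step 1: the plan's own figure.** The distance from the assumed truth to the margin is 4 - 1 = 3 points.

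- n per arm = 2 × (1.645 + 0.842)² × 15² / 3² = 309.1, rounded up to 310, or 620 in total. This matches.
- SE = 15 × √(2/310) = 1.205. Power = Φ(3/1.205 - 1.645) = 80.1%.

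The stated 80% therefore needs no covariates.

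**Step 2: the effect of prognostic covariates.** SE = 15 × √(1 - R²) × √(2/310); half-width = 1.645 × SE; power = Φ(3/SE - 1.645). The few degrees of freedom used by the extra terms are ignored.

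| R² (assumed) | SE | 90% half-width | Power | Total N for 80% power |
|---|---|---|---|---|
| 0 | 1.205 | 1.98 | 80.1% | 620 |
| 0.05 | 1.174 | 1.93 | 81.9% | 588 |
| 0.10 | 1.143 | 1.88 | 83.6% | 558 |
| 0.20 | 1.078 | 1.77 | 87.3% | 496 |

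**Step 3: is chance imbalance a further cost?** The standard error of a standardised baseline difference is √(2/310) = 0.080. With an assumed covariate-score correlation of 0.3, an imbalance of one standard error moves the unadjusted difference by 0.080 × 0.3 × 15 = 0.36 points. That equals 0.3 × 1.205, a component of the sampling error already inside the unadjusted interval. Adjusting removes it, and that removal is the gain in Step 2 at R² = 0.3² = 0.09. The two must not be added together.

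**Step 4: which variables each description contains.**

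| Variable | 9.4 | 7.2 via 9.1 | Footnote, Tables 5a/5b |
|---|---|---|---|
| Site | yes | not listed (fixed by 7.4) | yes |
| Child sex | no | optional | yes |
| Breastfeeding, stunting, family care | no | optional | yes |
| Weight | no | optional | no |
| Maternal age, education, gravidity, previous loss, BMI | no | no | no |

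Section 7.2 does not say whose weight it means. Standing beside stunting, it is read here as the child's.

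**The case against.** The best defence is that adjusting for the randomisation stratification factor alone is valid, that the sample size was built on such an analysis, and that it meets its target. Further covariates are then an efficiency preference, and the benefit rests on an R² that nobody has documented. At 0.05 it is 1.8 points of power. Between-site differences in maternal background are already absorbed by the site terms, so only within-site prediction counts. All of this stands, and it limits the size of the point. It does not explain why three sections describe three models.

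A reader might infer several stronger things that the documents do not support:

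- **That the plan is firmly site-only and ignores child sex.** Sex is a 7.2 candidate, is in the table-footnote model and is monitored at enrolment.
- **That baseline imbalance is left wholly uncorrected.** Section 7.2 allows adjustment, though not for any listed maternal variable.
- **That no model could ever use maternal data.** Protocol 3.1.2 foresees confounder-adjusted estimates for exploratory binary outcomes without naming the confounders. The supportable statement is that no listed covariate set names a maternal baseline variable.
- **That the selection of about 620 children has biased the comparison.** SAP 4.4 keeps research staff blinded, and SAP 4.3 has the coordinating centre review balance. Imbalance in maternal background is possible, but the documents neither show it nor allow it to be sized.

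**Conclusion.** The point holds as one of consistency and unused precision. The SAP gives three accounts of the covariates in the model that decides non-inferiority, the data-driven one has no threshold, and most of its candidates arise after randomisation. Maternal baseline variables carried over from the main trial are in none of the lists.

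It is not a power failure: the design figure reproduces. Nor does the 0.36-point chance shift amount to a bias of 9% of the margin, as a reader might take it to be. The gain is about 2 to 7 points of power over R² 0.05 to 0.20. That range is an assumption, and so is SD 15 as the residual SD after site, since the documents give 15 for the score overall. If site explains part of that variance, power before adjustment is already somewhat above 80.1%. The direction of the gain is secure when the covariates predict the score; its size is not known from the documents. The change is worth making because it costs little and settles the primary model.

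**What to change.** In SAP 9.4, state one primary ANCOVA: treatment, site, child sex, maternal education (as categories), maternal age, and maternal BMI as recorded at baseline in the main trial. Use it whatever imbalance is observed. Section 8.3 does not say when BMI was measured, so confirm that it predates randomisation. State how missing baseline values are handled so that no child is dropped, for example a missing category for education and mean imputation for age and BMI. Keep the site-only model as a sensitivity analysis.

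Then align the rest:

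- Delete the imbalance trigger in 7.2, and keep breastfeeding, stunting, weight and family care indicators for the modifying and mediation analyses already announced there.
- Correct the cross-reference in 9.1.
- Rewrite the footnote to Tables 5a and 5b to match 9.4.
- Leave out of the primary model the 8.3 items that arise after randomisation: antenatal visits, and the attendant, place and type of delivery.

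The cost is one paragraph and a few matching edits before unmasking, which SAP 4.4 places after data lock. No new data collection and no additional children are needed.

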9.5 Secondary Outcome Analyses

For ASQ and any other continuous outcomes, modeled-based analyses similar to the primary analysis will be used to generate estimated treatment effects (i.e., ANCOVA models used to obtain adjusted mean differences controlling for site). For binary outcomes, robust Poisson regression models will be used controlling for site in order to obtain relative risk estimates and associated confidence intervals. All models will be repeated including terms for region and its interaction with treatment to get region specific estimates of treatment effect.

10. SAFETY ANALYSIS:

No formal safety analyses are planned as a part of this study, although SAEs will be summarized. No formal hypothesis tests will be conducted, but descriptive p-values generated using Cochran-Mantel-Haenszel statistics with stratification by GN site will be generated.

11. CHANGES TO THE ANALYSES PLANNED IN THE PROTOCOL

No changes.

14. ATTACHMENTS

Updates to these tables will not require an analysis plan amendment.

Table 1 Participant Distribution

Table 2	Covariate Summaries
Table 3	BSID-III Outcome Descriptive Statistics
Table 4	ASQ Outcome Descriptive Statistics
Table 5a	BSID-III Adjusted Mean Estimates
Table 5b	BSID-III Adjusted Risk Ratio Estimates
Table 6a	ASQ Adjusted Mean Estimates
Table 6b	ASQ Adjusted Risk Ratio Estimates
Figure 1	Consort Diagram

Table 1. Participant Distribution

Variable	Overall		DRC		Zambia		Belagavi, India		Nagpur, India		Pakistan		Guatemala	
	Aspirin	Placebo	Aspirin	Placebo	Aspirin	Placebo	Aspirin	Placebo	Aspirin	Placebo	Aspirin	Placebo	Aspirin	Placebo
Screened														
Ineligible														
Eligible														
Enrolled														
BSIDS III completed														
Within age required														
ASQ completed														
Within age required														

Table 2: Covariate Summaries

Variable	Overall		DRC		Zambia		Belagavi, India		Nagpur, India		Pakistan		Guatemala	
	Aspirin	Placebo	Aspirin	Placebo	Aspirin	Placebo	Aspirin	Placebo	Aspirin	Placebo	Aspirin	Placebo	Aspirin	Placebo
Gender, n (%)														
Male														
Female														
Gestational age at delivery, n (%)														
< 37														
>= 37														
Breastfed after delivery														
Yes														
Months breastfed, mean (sd)														
No														
Stunting														
Yes														
No														
Family Care Indicators														
Books, mean (sd)														
Variety of play materials score (Q3-Q5), mean (sd)														
Sources of play materials score (Q7-Q13), mean (sd)														
Play activities score (Q14-Q23), mean (sd)														

Table 3: BSID-III Outcome Descriptive Statistics

Variable	Overall		DRC		Zambia		Belagavi, India		Nagpur, India		Pakistan	
	Aspirin	Placebo	Aspirin	Placebo	Aspirin	Placebo	Aspirin	Placebo	Aspirin	Placebo	Aspirin	Placebo
Evaluated on BSID III												
Age at Examination, N												
Mean (SD)												
Median (P25, P75)												
Minimum - Maximum												
Cognitive Test Results												
Language Test Results												
Motor Test Results												
Scaled Scores												
Cognitive Scaled Score, N												
Mean (SD)												
Median (P25, P75)												
Minimum - Maximum												
Receptive Language Scaled Score, N												
Mean (SD)												
Median (P25, P75)												
Minimum - Maximum												
Expressive Language Scaled Score, N												
Mean (SD)												
Median (P25, P75)												
Minimum - Maximum												
Summed Language Scaled Score, N												
Mean (SD)												
Median (P25, P75)												
Minimum - Maximum												
Fine Motor Scaled Score, N												

Mean (SD)												
Median (P25, P75)												
Minimum - Maximum												
Gross Motor Scaled Score, N												
Mean (SD)												
Median (P25, P75)												
Minimum - Maximum												
Summed Motor Scaled Score, N												
Mean (SD)												
Median (P25, P75)												
Minimum - Maximum												
Composite Scores												
Cognitive Composite Score, N												
Mean (SD)												
Median (P25, P75)												
Minimum - Maximum												
Language Composite Score, N												
Mean (SD)												
Median (P25, P75)												
Minimum - Maximum												
Motor Composite Score, N												
Mean (SD)												
Median (P25, P75)												
Minimum - Maximum												
Low Composite Scores												
Cognitive Composite Score <85												
Language Composite Score <85												
Motor Composite Score <85												

Table 4: ASQ Outcome Descriptive Statistics

Table 5a: BSID-III Adjusted Mean Estimates

Variable	Adjusted ¹ Mean (95% CI)		
	Aspirin	Placebo	Difference
BSID III Composite Scores			
Cognitive Composite Score			
Language Composite Score			
Motor Composite Score			
BSID III Scaled Scores			
Cognitive Scaled Score			
Receptive Language Scaled Score			
Expressive Language Scaled Score			
Summed Language Scaled Score			
Fine Motor Scaled Score			
Gross Motor Scaled Score			
Summed Motor Scaled Score			

Table 5b: BSID-III Adjusted Risk Ratio Estimates

	Aspirin n (%)	Placebo n (%)	RR (95% CI)
BSID III Composite Scores			
Cognitive Composite Score <85			
Language Composite Score <85			
Motor Composite Score <85			

1. Mean estimates and 95% confidence intervals from a regression model adjusting for site, gender, breast feeding, stunting and family care indicators.

Table 6a: ASQ Adjusted Mean Estimates

Variable	Adjusted ¹ Mean (95% CI)		
	Aspirin	Placebo	Difference
ASQ Total Score			
Communication total score			
Gross motor total score			
Fine motor total score			
Problem solving total score			
Personal-social total score			

Table 6b: ASQ Adjusted Risk Ratio Estimates

	Aspirin n (%)	Placebo n (%)	RR (95% CI)
ASQ Scores Below Cut Off			
Communication total score < 27.93			
Gross motor total score < 30.68			
Fine motor total score < 35.39			
Problem solving total score < 16.71			
Personal-social total score < 32.53			

1. Mean estimates and 95% confidence intervals from a regression model adjusting for site, gender, breast feeding, stunting and family care indicators.

Figure 1: Consort Diagram

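### SAP 9.4 names a site-adjusted ANCOVA with a 90% CI as the decision model, but 9.1, 7.2 and 7.5 leave it open and no table shell reports it

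*Combined protocol and SAP*

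**What the plan says.** **Decision model.** SAP 9.4 gives the rule: "If the lower bound of the 90% confidence interval is greater than -4, then the treatment is assumed to be non-inferior to placebo". On the model it says "All analyses will be modeled based controlling for site as the original randomization stratification factor", and it commits to reporting: "the adjusted mean difference between treatment groups and the associated 90% confidence interval based on an ANCOVA model will be calculated and presented". Sections 7.4 and 9.5 also name site as the adjustment factor.

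**Covariates elsewhere.** SAP 9.1 states: "All model-based analyses and test-statistics examining the treatment effect will adjust for covariates as specified in sections 7.2 and 7.3". Section 7.2 is permissive: "covariates may be adjusted for in the analyses if treatment imbalance is present". Its list reads: "Covariates for consideration include gender, breast feeding, stunting, weight, and family care indicators". It then adds: "These factors will also be explored in secondary analyses for modifying/mediation effects". Section 7.3 deals with missing data and names no covariate.

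**Error level.** Section 6 powers non-inferiority as a one-sided 5% test, which matches the 90% interval in 9.4. Section 7.5 says there is one formal test and puts the primary measure at 5% two-sided.

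**Shells.** In section 14, the Table 5a column header gives 95% intervals. The footnote marked on Tables 5a and 6a describes "Mean estimates and 95% confidence intervals from a regression model adjusting for site, gender, breast feeding, stunting and family care indicators". Section 14 also allows the shells to be changed without amending the SAP.

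**The concern.** Read alone, 9.4 is clear. The trouble is what surrounds it. Under 9.1 and 7.2, an analyst could add covariates to the confirmatory model after seeing how the arms compare, with no definition of imbalance and no rule for which variables enter. The choice of model would then depend on the data.

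One candidate is stunting. Mothers were randomised during pregnancy, so any measure of child growth comes after randomisation. The SAP lists anthropometry among its other outcomes (3.3) and treats the 7.2 covariates as possible mediators. A model that conditions on stunting may therefore not estimate the total effect of antenatal aspirin, which is what the hypothesis names.

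The decision result also has no place in the planned output. A reader of Table 5a would see a different model and a wider interval than those behind the non-inferiority conclusion.

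**Working it through.** **1. The SAP text side by side**

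| Place in SAP | Covariates | Interval or level | Force |
|---|---|---|---|
| 9.4 (7.4 and 9.5 agree on site) | site | 90% CI, lower bound against -4 | decision rule; to be presented |
| 9.1, pointing to 7.2 and 7.3 | 7.2: gender, breast feeding, stunting, weight, family care; 7.3: none | none | 9.1 mandatory; 7.2 optional, on imbalance |
| 7.5 | none | 5% two-sided | the one formal test |
| Table 5a footnote | site, gender, breast feeding, stunting, family care | 95% CI | unconditional, but shell can change |

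Site is in 7.4, so the reference to 7.3 in 9.1 looks like a slip for 7.4. None of the listed shells (Tables 1 to 6b) has a site-adjusted difference with a 90% CI.

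**2. The plan's own figure.** Inputs from section 6 and the protocol: SD 15, margin 4, true difference -1, one-sided 5%, 80% power. SAP section 6 prints the SD as 15.47. This looks like the protocol's reference number 47 run into the 15: an SD of 15.47 would need 329 per arm, whereas 15 gives the stated size.

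- n per arm = 2 × 15² × (1.645 + 0.842)² / (4 - 1)² = 309.1, so 310, or 620 in total.
- SE = 15 × √(2/310) = 1.205.
- Power at -1 = Φ(3/1.205 - 1.645) = 80.1%.

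The stated size and power reproduce, and they belong to the 90% interval.

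**3. Illustration: the same rule read from a 95% interval, same SE**

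- Half-widths: 1.645 × 1.205 = 1.98 (90%); 1.960 × 1.205 = 2.36 (95%).
- Estimate needed: -4 + 1.98 = -2.02; -4 + 2.36 = -1.64.
- Power at a true -1 with 95%: Φ(3/1.205 - 1.960) = 70.2%.

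**4. Allowing for covariates.** Table 5a is a covariate-adjusted model, so its SE should be smaller. Assume that the extra covariates explain 5% to 15% of the variance left after site; the documents give no figure.

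- SE = 1.205 × √(1 - R²) = 1.174 to 1.111.
- Power at -1 with 95%: Φ(3/1.174 - 1.960) = 72%, to Φ(3/1.111 - 1.960) = 77%.
- Power at -1 with 90%: 81.9% to 85.4%, which is about 2 to 5 points above 80.1%. This is the precision forgone by a site-only primary model.

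**5. Stunting.** The SAP does not define it. The only child height measurement described is on the Medical History form (protocol 2.4.5 and section 4), taken at the 33-39 month visit. The documents give neither an effect of aspirin on stunting nor a link from stunting to scores within this cohort, so the effect of adjusting cannot be sized or signed. By this route it is zero if aspirin does not affect growth. The follow-ups cited in protocol 1.4.3.1 differ: the largest found no anthropometric difference, while an unblinded one reported fewer exposed children below the 10th percentile for height.

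**The case against.** **The SAP already has a decision model.** A reader might infer that it contradicts itself on which model decides. That goes too far. Section 9.4 is specific, 7.4 and 9.5 agree with it on site, and 7.2 only permits adjustment. A permissive clause does not set up a rival rule. What stands is that 9.1 covers all treatment-effect models without exception, so the discretion in 7.2 reaches the confirmatory one.

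**The shells are weak evidence.** They can change without amendment and are visibly incomplete: none is listed for the per-protocol analysis, the region-specific estimates or the SAE summary. Protocol 3.1.2 plans unadjusted and confounder-adjusted estimates for exploratory binary outcomes, so Table 5a may be meant as a supportive display. That is a fair reading. But the table is not labelled so, and the promised 90% interval still has no table.

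**The power figures could be over-read.** A reader might infer that the trial has only 70% power. Nothing in the SAP applies the -4 rule to Table 5a, and the 70.2% uses an SE without the table's covariates.

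**Stunting is a recognised confounder.** Protocol 1.3 lists it among potential confounders, but asks that these be documented; it does not place them in the confirmatory model. Conversely, a reader might infer that adjusting for stunting biases the result. The documents support only the possibility.

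**Section 7.5 may have superiority in mind.** Section 6 does use a two-sided 5% test for that step. But 7.5 does not say so, and 9.4 runs superiority one-sided.

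**Conclusion.** The point holds as a failure to close off and report the decision model, and it should be fixed. Section 9.4 sets that model. Sections 9.1 and 7.2 leave room for a data-dependent version that could contain a possible mediator, 7.5 gives a different error level, and no shell shows the result that decides.

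The sample size is not in question: 620 children give 80.1% power with the 90% interval, assuming SD 15 and a true difference of -1. Reading the -4 rule from a 95% interval would give 70.2% at the planning SE, or about 72% to 77% if covariates explained an assumed 5% to 15% of the remaining variance. Both are conditional illustrations of why the interval must be unambiguous, not predictions of how the trial will be analysed. No figure can be given for adjusting for stunting. No point is made about weight, because 7.2 does not say whose weight it means or when it is measured.

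**What to change.** Make these changes before unmasking, which SAP 4.4 places after data lock:

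1. State in 9.1 and 9.4 that the single decision model is the site-adjusted ANCOVA with its 90% CI, and correct the reference to 7.3 in 9.1 to 7.4. This belongs in the SAP text because the shells can change freely.
2. Remove the imbalance trigger in 7.2 from the confirmatory analysis.
3. Align 7.5 with the one-sided 5% non-inferiority test of section 6 and 9.4.
4. Make the site-adjusted difference with its 90% CI the primary row of Table 5a.
5. Label the covariate-adjusted model in Tables 5a and 6a as supportive, with its covariates fixed in advance. Report any model with stunting or other post-randomisation growth only as exploratory or mediation analysis.
6. Breast feeding and family care indicators also arise or are recorded after randomisation and fall under the same mediation sentence in 7.2. State in advance whether, and why, each stays in the supportive model.

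The cost is wording, one table row and footnotes. No new data and no change in sample size are needed. The price is the small loss of precision in the primary model shown in step 4 of the working. A prespecified supportive model still serves the protocol's wish to adjust for local context.
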